## 1 PROTOCOL SUMMARY

### 1.1 SYNOPSIS

Title:	Development of a Novel Transdiagnostic Intervention for Anhedonia
Study Description:	
The overall goal of this project is to develop a novel transdiagnostic treatment for anhedonia, called Behavioral Activation Treatment for Anhedonia (BATA), using ultra-high field functional neuroimaging. There is a critical need for a validated treatment that specifically targets anhedonia, and this project will evaluate the effects of this new treatment on anhedonia and will establish how this treatment impacts brain systems that mediate reward processing, clinical symptoms of anhedonia, functional outcomes, and behavioral indices of reward processing. During the first phase of the study (R61-i.e., the first 60 participants), both groups will receive pre- and post-treatment scans as well as two mid-treatment scans (weeks 8 and 12) to evaluate treatment dose (4 scans total). During the second phase of the study (R33-i.e., the remaining 150 participants), participants will receive only pre- and post-treatment scans (2 scans total). All participants will complete interview, symptom, and behavioral measures before and after treatment. PET supplement: 30 participants that are part of the main parent NIMH grant will be asked to enroll in the PET sub-study & complete up to 2 PET scans pre/post during the study. It is optional, so participants may refuse & still participate in the main study. Of the 30 enrolled in the PET sub-study, ~50% will be randomized to the investigational treatment BATA & ~50% to the control condition, MBCT.
 
R61 Phase: Aim 1: To evaluate whether BATA produces changes in neural responses to reward anticipation and reward outcomes using fMRI that exceed changes due to an active comparison treatment, specifically

Objectives:	

*Mindfulness Based Cognitive Therapy (MBCT) and does not impact neural responses to threat. This aim pertains to only the first 60 participants randomized into the study (n=30 to receive BATA and n=30 to receive MBCT). **Aim 2:** To evaluate relations between BATA dose (treatment duration) and neural target engagement by examining changes in neural response to rewards with mid-treatment fMRI scans 8 and 12 weeks after starting the 15-week treatment.*

*R33 phase of this grant, pertains up to 210 participants in the study (105 randomized to BATA & 105 randomized to MBCT):*

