**Aims 3, 4, and 5 pertain to all 210 participants randomized (n=105 to receive BATA and n=105 to receive MBCT).**

**Aim 3:** To evaluate the effects of BATA versus an active comparison treatment on anhedonic symptoms and functional outcomes.

**Aim 4:** To evaluate the effects of BATA versus an active comparison treatment on behavioral indices of reward sensitivity.

**Aim 5:** To evaluate the effects of BATA versus a comparison treatment on neural response to rewards.

PET Aims specifically refer to the 30 subjects who consent to the optional PET sub-study:

**Aim 1 (PET):** To evaluate the effects of BATA, relative to a comparison treatment, on PET-derived measures of DA functioning during incentive processing. We hypothesize that BATA, but not the comparison treatment, will result in increased phasic striatal DA release but will not influence background DA striatal tone.

**Aim 2 (PET):** To evaluate relations between treatment-related changes in fMRI-derived mesocorticolimbic activation and PET-derived DA functioning in the BATA-treated group. We hypothesize that normalization of fMRI-derived mesocorticolimbic activation due to BATA specifically will be associated with increased phasic DA release but no change in background DA tone during incentive processing.

Exploratory Aims include the data from the EMA optional study: Passive location tracking (PLT) data during the period of EMA monitoring will be collected via the MetricWire app to allow us to compare distance traveled before and after both treatments as a secondary, exploratory measure of behavioral activation. Follow-up analyses will evaluate relations between motion tracking, behavioral, brain, and clinical measures of response to both treatments.

**Specific Aim 3 (EMA):** To evaluate if BATA, relative to a comparison treatment, produces improvements in real-world positive affect and the use of BATA skills. We hypothesize that BATA, but not the comparison treatment, will be associated with improvements in real-world positive affect and the use of BATA skills.

**Specific Aim 4 (EMA):** To evaluate relations between treatment-related changes in fMRI-derived mesocorticolimbic activation and real-world positive affect and the use of relevant BATA skills in the

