**Aims 3, 4, and 5 pertain to all 210 participants randomized (n=105 to receive BATA and n=105 to receive MBCT).**

Aim 3: We predict that BATA will produce clinically and statistically significant improvements in anhedonia and functional outcomes that exceed those due to the comparison treatment.

Aim 4: We predict that BATA will improve behavioral indices of reward sensitivity.

Aim 5: To evaluate the effects of BATA versus a comparison treatment on neural response to rewards. We predict that, consistent with Aim 1, BATA will increase right CN activation during reward anticipation and decrease rACC activation during reward outcomes and that BATA will not decrease amygdala activation to threat, confirming the specificity of BATA for targeting these positive valence neural systems. This Aim will provide a replication and extension of Aim 1 findings with a larger sample and with an optimal treatment dose.

In the PET sub-study, Hypothesis 1- BATA, but not the comparison treatment, will result in increased phasic striatal DA release but will not influence background DA striatal tone. Hypothesis 2- that normalization of fMRI-derived mesocorticolimbic activation due to BATA specifically will be associated with increased phasic DA release but no change in background DA tone during incentive processing.

This is not a pilot study but rather a Phase I/II study. The R61 phase (Phase I) of the protocol is designed to provide preliminary data for the acceptability, identification of the optimal dose of BATA as well as the preliminary efficacy of BATA in subjects with anhedonia compared to those in the MBCT control group. Using the fMRI data, this phase of the study will test if BATA produces changes in neural responses to reward anticipation and reward outcomes that exceed changes in the MBCT group and does not impact neural responses to threat. As such, a small group (N = 60) of subjects will be in this blinded phase and they will complete up to a total of 4 fMRI scans (pre-treatment, week 8, 12 and post-treatment). The R61 study will be entering a no-cost extension at the end of the current project period to allow for completion of data collection for this phase. Due to limited funds, the number of scans obtained is being reduced from up to 4 scans to two scans (pre- and post-treatment.) for participants

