**PET Power Analyses:** Sample sizes are dictated by the limitations of this funding mechanism, and we note that the majority of published molecular imaging studies have had relatively modest sample sizes. We also note that one advantage of our approach is that both phasic and tonic DA states are acquired during the same scan, thereby allowing for statistical models that use within-subjects variance calculations. Finally, we highlight that the test-retest stability of [11C]raclopride-derived DA binding potentials is very good (ICC = .82 for the NAcc [46]). Our power analysis is based on power to detect group differences in the intra-subject correlation between DA release and change in BOLD signal. Assuming a standard deviation in DA-mediated binding potential changes of 0.3 (approximately 10%), we will be powered to detect a  $>15\%$  change in DA binding (?BP%) with a power of 0.85 and a false discovery rate of 2.5%. This sample size is limited by the funds available through this grant mechanism and the extremely high cost of PET imaging.

*EMA Power Analysis.* Given our sample size, we consider EMA to be preliminary data that may be used to estimate effect sizes for future grant applications that use EMA as an outcome measure for anhedonia clinical trials. Additionally, the proposed structural equation models are very complicated and may need to be adjusted. With the sample size of the R61 phase of the parent grant, the proposed analyses should have medium power (50% or more) to identify paths if the paths correspond to partial correlations of  $|0.10|$  or larger. By continuing to collect EMA data in R33, we hope to increase our sample size and also explore changes after wk 4, 8, and 12 (if applicable) computer tasks, thus EMA is not only linked to pre- and post treatment MRI scan visits.

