**PET Analysis:** The primary PET metrics to be evaluated will be striatal background DA tone and phasic DA release. Study UNC biostatistician will oversee all analyses. UNC will first evaluate the means and standard deviations of PET-derived striatal binding potentials. **Aim 1** (to evaluate relations between BATA response and PET-derived changes in background DA tone and phasic DA release) will be evaluated by extracting the dynamic change in binding potential ( BPND%) before, during and after the task and then comparing these values before and after treatment between treatment groups. **Aim 2** (to evaluate relations between BATA related changes in fMRI and PET-derived background DA tone and phasic DA release) will be addressed by correlations between changes in PET striatal binding potential magnitudes and changes in fMRI.

**EMA: Primary Analyses**-For EMA, the primary variables of interest will be scores on the positive/negative affect and anhedonia items over the assessment periods. Given the longitudinal (i.e., repeated waves of EMA data) and hierarchical (i.e., assessment timepoints nested within individuals) structure of the data to be collected, Hierarchical Linear Modeling (HLM) will be used to analyze EMA data.

Follow-up analyses with the Passive location tracking of MetricWire will evaluate relations between motion tracking, behavioral, brain, and clinical measures of response to both treatments. **Optional EMA enrollment ended with the NCE June 2022 amendment.**

---

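### The PET sub-study predicts that BATA leaves background dopamine tone unchanged, but the plan has no criterion for supporting an absence of effect, and about 12 to 15 people per arm can exclude only large changes

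*Combined protocol and SAP*

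**What the plan says.** Section 3, Aim 1 (PET), hypothesises that BATA, unlike the comparison treatment, "will result in increased phasic striatal DA release but will not influence background DA striatal tone". Aim 2 (PET) hypothesises that normalisation of fMRI activation "will be associated with increased phasic DA release but no change in background DA tone during incentive processing". Both statements recur in Sections 1.1 and 4.1. Each has two halves: a predicted change in phasic release and a predicted absence of change in tone.

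Section 9.2 (PET Analysis) gives tone equal standing within the sub-study: "The primary PET metrics to be evaluated will be striatal background DA tone and phasic DA release". For Aim 1 it extracts the dynamic change in binding potential around the task and then proceeds by "comparing these values before and after treatment between treatment groups". For Aim 2 it correlates PET changes with fMRI changes. Nothing further is specified for either aim.

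On size, Section 3 states: "PET Aims specifically refer to the 30 subjects who consent to the optional PET sub-study". Section 1.1 adds: "Of the 30 enrolled in the PET sub-study, ~50% will be randomized to the investigational treatment BATA". Section 9.1 is open about the constraint: "Sample sizes are dictated by the limitations of this funding mechanism". Its power statement is framed around a group difference in the correlation between dopamine release and BOLD. It then claims power of 0.85 for a change above 15%, given an SD of about 10% and an error rate of 2.5%. It does not address ruling out a change in tone.

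**The concern.** A hypothesis of no influence is a claim of absence. A difference test can count against it but cannot support it: a non-significant result may mean that tone did not move, or that the sample was too small to show that it did. Supporting absence needs a statement of how small a change would count as none, and an interval narrow enough to exclude anything larger. The plan has neither.

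At stake is the mechanistic conclusion the sub-study is built around, that BATA acts on phasic release and leaves tone alone. A significant phasic result beside a non-significant tone result would not establish that the two effects differ, yet the pair would look like the predicted pattern. Section 2.3.2 presents the PET results as preliminary data for later proposals, so an unsupported claim of selectivity could carry forward.

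**Working it through.** **Inputs**
- 30 enrolled, about half per arm (Sections 1.1 and 3): about 15 per arm.
- Retention of 81% between pre- and post-treatment imaging (Section 5.4): 15 × 0.81 = 12.15, about 12 per arm with both scans. Section 5.4 gives this for psychotherapy trials with neuroimaging; applying it to PET is my assumption.
- SD of binding-potential change about 10%, detectable change 15%, ICC .82 (Section 9.1). The SD is given for dopamine-mediated changes; using it for tone is an assumption.
- Benchmark of 0.5 SD: mine, not the plan's. Two-sided alpha 0.05 unless stated.

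**The plan's own power figure.** The effect is 15/10 = 1.5 SD. A two-group t-test at two-sided 0.025 has power 0.95 with 15 per arm and 0.89 with 12. The stated 0.85 is matched at 11 per arm (0.853), a number the plan does not give. The test, the sidedness and the analysed n are not stated, so the figure is untraceable rather than wrong. Nothing below depends on it.

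**Probability of missing a true difference in tone change.** Two-sample noncentral t, df = 2n − 2, noncentrality = d × √(n/2). For d = 0.5 this is 1.22 at n = 12 and 1.37 at n = 15.

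To place 0.5 SD on the between-person scale, the SD of change is √(2(1 − .82)) = 0.60 between-person SD, so d = 0.5/0.60 = 0.83.

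| True difference | Between arms, n = 15 / 12 | Within BATA (paired), n = 15 / 12 |
|---|---|---|
| 0.5 SD of change | 74% / 78% missed | 56% / 65% missed |
| 0.5 between-person SD (0.83 SD of change) | 40% / 50% missed | 15% / 25% missed |
| 1.5 SD of change (the plan's 15%) | 2% / 6% missed | under 1% missed |

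**What an interval could exclude.** The 90% CI half-width for the arm difference is t(.95, 2n − 2) × √(2/n).
- n = 15: 1.701 × 0.365 = 0.62 SD.
- n = 12: 1.717 × 0.408 = 0.70 SD.

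With an SD of 10% this is about 6-7% in binding potential. If the true difference is zero, two one-sided tests at 0.05 would meet a margin of ±0.5 SD less than 1% of the time, ±1.0 SD 54-70% of the time (12 to 15 per arm), and ±1.5 SD 94-98% of the time. A ±0.5 SD margin would need about 69 per arm for 80% power (normal approximation).

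**Hypothesis 2.** In a BATA arm of 15 to 12 people, simulation with 100,000 replicates shows that a true correlation of .3 with tone change is missed 81-84% of the time, and one of .5 is missed 50-60% of the time.

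**The case against.** Five points can be made for the plan.

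1. **A reader might infer that the team will take non-significance as proof of no effect.** The documents do not say so. Section 9.2 says that values will be compared and correlated, and stops there. The confirmatory language about specificity in Section 4.1 is attached to the amygdala prediction, not to PET tone. What stands is narrower: no other route to support is provided.

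2. **A reader might infer that a half-SD change would usually be missed.** That holds only on the SD-of-change scale. With the plan's ICC, such a change is usually detected within BATA and is close to a coin-flip between arms. At the plan's own 15% it would almost always be seen. The sub-study is therefore not blind to tone changes; it cannot exclude moderate ones.

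3. **A reader might infer that a phasic-versus-tonic comparison was overlooked.** Section 9.1 notes that both states come from the same scan and that this permits within-subject models, and the before/during/after layout in Section 9.2 contains the necessary contrast. It is contemplated but not specified.

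4. **The status is modest.** Tone is a primary metric only inside an optional sub-study. Section 1.1 lists the PET endpoints after the secondary and exploratory heading, and the go/no-go decision rests solely on the 7T region-of-interest analysis (Section 9.2). This stands and governs the severity.

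5. **The remedy is limited.** Section 4.2 records the last PET scan on 7/7/21, so the sample cannot grow, and the documents do not show whether a margin can still be set before analysis. This stands too, and it shapes the fix. It does not remove the need for a rule on how the tone result is worded.

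**Conclusion.** The point holds in a limited form and is minor. The plan states a no-influence hypothesis for one of its two main PET metrics and gives no criterion by which it could be supported. That gap does not depend on any benchmark.

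Its size does. At 12 to 15 per arm and two-sided 0.05, the between-arm miss rate is 74-78% for 0.5 SD of change, 40-50% for 0.5 between-person SD, and 2-6% for the plan's 1.5 SD. These figures assume equal arms, roughly normal changes, and, for the lower n, that 81% retention applies to PET. The documents do not support saying that the investigators will misread a null result, that every half-SD change would usually be missed, or that the stated power of 0.85 is wrong. No trial decision rests on the tone result.

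**What to change.** In Section 9.2 (PET Analysis):

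- State that absence of an effect on tone will not be concluded from a non-significant test.
- Say which binding-potential measure represents background tone, and report the BATA-minus-MBCT difference in its pre/post change with a confidence interval.
- Describe the result as no evidence of change, with changes up to the interval limits not excluded, unless the 90% CI lies inside a margin justified and fixed before the tone data are analysed. If the analysis has already been done, report the interval and make no equivalence claim.
- Base any claim that phasic and tonic effects differ on a direct within-subject contrast (task phase × time × arm, or standardised changes), using the same-scan data that Section 9.1 describes.

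Reword the tone half of Hypotheses 1 and 2 in Sections 1.1, 3 and 4.1 to match.

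The cost is a few sentences plus one interval and one contrast on data already collected. The downside is that the tone result will probably be reported as inconclusive.

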### 4 STUDY DESIGN & PROCEDURES

#### 4.1 OVERALL DESIGN

The clinical objective of this project is to evaluate Behavioral Activation Treatment for Anhedonia (BATA), a novel psychotherapy designed to treat anhedonia using an experimental therapeutics approach in a transdiagnostic sample characterized by clinically impairing anhedonia. BATA is a modification of Behavioral Activation Therapy for Depression, a validated treatment for patients with mood disorders. We have extensively modified this treatment to treat anhedonia in a transdiagnostic sample in a manner that is consistent with research domain criteria (RDoC) priorities. We propose to evaluate mesocorticolimbic response to rewards versus threat by BATA versus Mindfulness-Based Cognitive Therapy (MBCT) on anhedonia symptoms, functional outcomes, behavioral indices of reward sensitivity, and neural responses to rewards versus threat.

**Aims 1 and 2 pertain to the first 60 participants randomized (n=30 to receive BATA and n=30 to receive MBCT).**

Aim 1: We predict that BATA will increase right caudate nucleus (CN) activation during reward anticipation and decrease rostral anterior cingulate cortex (rACC) activation during reward outcomes, and that BATA will not decrease amygdala activation to threat, confirming the specificity of BATA to these positive valence neural systems.

Aim 2: We predict that the BATA group will show increased right CN activation during reward anticipation and decreased rACC activation during reward outcomes that will plateau after the optimal dose of the intervention has been delivered.

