Description of Study Intervention:	BATA: modified Behavioral Activation Treatment for Depression to create Behavioral Activation Treatment for Anhedonia (BATA). Treatment in the R61 phase (Phase I) will consist of up to 15 weekly 45-minute sessions. In the R33 phase, BATA sessions will again be from 8 to 15 weekly 45-minute sessions. BATA will be compared to MBCT (Mindfulness-Based Cognitive Therapy), chosen because its mechanisms of action are hypothesized to impact different brain mechanisms than BATA. To control for nonspecific factors in BATA including clinician contact, MBCT is administered in an individual format. MBCT in the R61 phase will be compromised of up to 15 weekly 45-minute sessions. In the R33 phase, the number of sessions match that of BATA.
Study Duration:	72 months
Participant Duration:	Three to five months

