#### **R61 Phase:**

**Aim 1:** To evaluate whether BATA produces changes in neural responses to reward anticipation and reward outcomes using fMRI that exceed changes due to an active comparison treatment, specifically Mindfulness Based Cognitive Therapy (MBCT) and does not impact neural responses to threat. This aim pertains to only the first 60 participants randomized into the study (n=30 to receive BATA and n=30 to receive MBCT).

**Aim 2:** To evaluate relations between BATA dose (treatment duration) and neural target engagement by examining changes in neural response to rewards with mid-treatment fMRI scans 8 and 12 weeks after starting the 15-week treatment.

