#### 4.3 SCIENTIFIC RATIONALE FOR STUDY DESIGN

This study and its design will deliver an empirically supported transdiagnostic anhedonia treatment as well as an fMRI-based quantitative index of mesocorticolimbic target engagement to use in future experimental therapeutics trials of novel anhedonia treatments. Testing whether the treatment impacts motivational circuitry specifically: The effects of many psychiatric treatments are non-specific.

Pharmacologic agents, including SSRI's, have relatively equivalent and moderate effects for a range of disorders [51], likely due to the fact that non-specific symptoms of general worry are targeted across disorders [52]. This proposal includes an fMRI task that is sensitive to the negative valence system construct of "threat" which includes anxious arousal, increased conflict detection, attentional bias to threat, and avoidance and recruits the amygdala, hippocampus, and insula. We will thus be able to distinguish the impact of BATA on brain systems that subserve motivation and pleasure from those that subserve threat. Aim 2 will include mid-treatment scans to determine the optimal BATA dose, and multilevel modelling will estimate the optimal number of sessions to achieve target engagement. In this way, we will be positional to evaluate the optimal dose of BATA in the R33 phase.

In the PET sub-study, because of the relatively slow kinetics of [11C]raclopride displacement, in the present study we will use a monetary incentive delay task that has been optimized for [11C]raclopride PET imaging (Schott et al., 2008). The task will be divided into rewarded (75% reward trials) and nonrewarded (0% reward trials) blocks that are each 18 minutes long.

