## 9 STATISTICAL CONSIDERATIONS

### 9.1 SAMPLE SIZE DETERMINATION

**Aims 1, 2, and 5:** To evaluate whether BATA produces changes in neural responses to reward anticipation and reward outcomes that (1) exceed our *a priori* target engagement criteria; (2) exceed changes due to a comparison treatment; and (3) does not impact neural responses to threat. To evaluate relations between BATA dose and neural target engagement by examining changes in reward responding with fMRI scans 8, 12 and 16 weeks after starting the 15-week treatment.

Power is calculated for Aim 1 fMRI analyses because of its smaller sample, and the Aims that involve all 210 participants will have higher power because of the larger sample and optimized BATA dose. For Aim 1 we will enroll 30 outpatients per group to have complete data from 25 per group. Based on our pilot data demonstrating increased right CN activation during reward anticipation and decreased rACC activation during reward outcomes, we calculated an effect size of approximately  $z=4.1$ . Conservatively, we estimate the effect size for the increased right CN activation and reduced rACC activation will be in the range of  $z = (0.75-1.25)$ . Our models will thus have  $>90\%$  power at  $\alpha=0.025$ .

**Aims 3 and 4:** To evaluate the effects of BATA versus MBCT on anhedonic symptoms, functional outcomes, and behavioral indices of reward sensitivity. Our power analysis addresses the effects of BATA versus MBCT on SHAPS scores (conducted with Gpower) as an ANCOVA with two groups and two timepoints. With 65 subjects per treatment group with complete data at post-treatment,  $\alpha = .05$ , and assumed correlation between assessments of 0.35 (based on preliminary studies), we will have 98% power to detect small ( $f = .2$ ) effects. Pilot data in depressed patients indicated a large effect from pre-to post-treatment ( $d=1.24$ ,  $f = .62$ ), and we are powered to detect these effects. We are 80% powered to detect the interactions with effects as small as  $f = .14$ .

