Exploratory Connectivity Analyses: Mesocorticolimbic connectivity in central to anhedonia. We will explore task-dependent correlations between ROIs using a psychophysiological interactions approach as in our prior work. Timeseries will be extracted from ROIs using FSL Featquery for each participant and trial type and correlation values will be transformed using a Fisher r-to z transformation. We also conduct whole-brain connectivity analysis, with a particular emphasis on the salience network (i.e., dorsal anterior cingulate cortex, anterior prefrontal cortex, and anterior insula), by segmenting the brain based on a probabilistic atlas, while correcting for multiple comparisons at the familywise error rate of  $p < .05$ .

**Secondary Analysis:** Secondary data analysis will be conducted examining relationship between psychological symptoms and patterns of brain activation in the functional neuro data. Data will be transferred from UNC to Duke to be analyzed by Duke study team members.

**Aims 1 and 5:** Only patients who complete baseline measures will receive BATA, and those who complete at least one BATA session will participate in post-treatment assessments (ITT, estimating ~90% of sample). We will compare fMRI activation in regions of interest at pre- and post-treatment. Primary analyses will address changes in regional brain activation from baseline to post-treatment.

Models will include motion parameters, gender, and age as covariates. The design is a 2 (BATA vs MBCT) X 3 (CN, rACC, amygdala) X 2 (pretreatment vs post-treatment) ANCOVA testing the change from pre- to post-treatment as moderated by treatment group and brain region in the outcome variables controlling for the covariates. Post-hoc comparisons will compare change across each region. Note that CN and rACC activation values are derived from the MID task whereas amygdala activation values are derived from the threat task.

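### Aims 1 and 5 read the absence of an amygdala decrease as proof of specificity, but the plan has only tests of difference and leaves the direction and comparison open

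*Combined protocol and SAP*

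**What the plan says.** Section 4.1 gives the Aim 1 prediction that "BATA will not decrease amygdala activation to threat, confirming the specificity of BATA to these positive valence neural systems". For Aim 5 it predicts, on the full sample, that "BATA will not decrease amygdala activation to threat, confirming the specificity of BATA for targeting these positive valence neural systems". Section 3 words Aim 1 differently: BATA "does not impact neural responses to threat". The Synopsis, the R61 description in Section 4.1 and the heading text of Section 9.1 also use the no-impact form. Section 4.3 relies on the threat task in the rationale: "We will thus be able to distinguish the impact of BATA on brain systems that subserve motivation and pleasure from those that subserve threat".

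For the analysis, Section 9.2 (Aims 1 and 5) states: "The design is a 2 (BATA vs MBCT) X 3 (CN, rACC, amygdala) X 2 (pretreatment vs post-treatment) ANCOVA", with motion, gender and age as covariates, and then: "Post-hoc comparisons will compare change across each region". The same section defines the amygdala region (Harvard-Oxford atlas) and the contrast (fearful and angry faces against shapes).

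Section 9.1 names the threat hypothesis among its aims, but its effect sizes cover the two reward regions only: "we estimate the effect size for the increased right CN activation and reduced rACC activation will be in the range of" 0.75 to 1.25. It gives more than 90% power at alpha 0.025 with 25 complete per group and does not state sidedness. The documents contain no amygdala margin, interval rule, Bayesian rule or power figure.

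**The concern.** The amygdala hypothesis succeeds if nothing happens. Every planned test asks whether something happened. With no other rule in the plan, a non-significant amygdala result could be reported as confirming specificity even when the estimate is too imprecise to exclude a sizeable fall.

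Two choices change what would have to be shown. One is direction: no decrease needs one confidence limit, while no impact needs both. The other is comparison: change within BATA and change relative to MBCT differ in precision and in meaning.

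What is at stake is one stated conclusion of Aims 1 and 5. The tests on CN and rACC are not affected.

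**Working it through.** **Inputs.** From the documents: 25 complete per arm (Section 9.1); 105 randomized per arm (Section 4.1); 81% retention between scans (Section 5.4), so 0.81 x 105 = 85; alpha 0.025; effects of 0.75 to 1.25 for CN and rACC. Assumed, because the documents give no figure: a true amygdala fall of 0.5 SD of change (0.3 to 0.6 also shown); an illustrative margin of 0.5 SD; and 60 per arm, because imaging of new participants stopped with the June 2022 amendment and the number scanned is not stated.

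**Step 1: the plan's own figure.** Section 9.1 does not name the test. Reading 0.75 as SD units:
- Within one arm, the noncentrality is 0.75 x √25 = 3.75 on 24 df. Two-sided 0.025 gives 90.5%, which matches.
- Between arms, it is 0.75 x √(25/2) = 2.65 on 48 df, giving 63.3%. More than 90% is reached only with an unstated pre-post correlation of about 0.66 or more.

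The stated power therefore reproduces for reward regions, most simply as within-arm change. It says nothing about the amygdala.

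**Step 2: how often a real fall is missed.** Miss rate = 1 - power from the noncentral t. The noncentrality is d√n within BATA (n - 1 df) and d√(n/2) between arms (2n - 2 df). For d = 0.5 and n = 25 these are 2.50 and 1.77. Each cell lists one-sided 0.05 / two-sided 0.05 / two-sided 0.025.

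| Complete per arm | Within BATA | BATA against MBCT |
|---|---|---|
| 25 | 21.7% / 33.0% / 44.9% | 46.1% / 59.0% / 69.8% |
| 60 (assumed) | 1.5% / 3.2% / 6.1% | 14.1% / 22.5% / 32.0% |
| 85 | 0.2% / 0.5% / 1.1% | 5.5% / 10.0% / 16.0% |

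Sensitivity:
- At 25 per arm, falls of 0.4 to 0.6 SD are missed 38% to 10% of the time within BATA (one-sided 0.05) and 72% to 45% between arms (two-sided 0.05).
- A 0.3 SD between-arm difference is missed 82% of the time at 25, 51% at 85 and 42% at 105 (two-sided 0.05).

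The 95% half-width at 25 per arm is 2.064/√25 = 0.41 SD within BATA and 2.011 x √(2/25) = 0.57 SD between arms. An interval centred on zero would not exclude a between-arm fall of 0.5 SD.

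**Step 3: do the planned region comparisons fill the gap?** Take CN +0.75, rACC -0.75, no change in MBCT and independent regions, so a region difference has SD √2. The noncentrality is (contrast/√2) x √(n/2). At 25 per arm, two-sided 0.05:
- CN minus amygdala: amygdala 0 gives 0.75/√2 x 3.54 = 1.88 and 45% rejection; amygdala -0.5 gives 1.25/√2 x 3.54 = 3.13 and 87%.
- rACC minus amygdala: amygdala 0 gives 45%; amygdala -0.5 leaves a contrast of -0.25, noncentrality -0.63, and 9%.
- Omnibus interaction (simulated): 91% with amygdala 0, and 94% to 95% with -0.5.

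At 85 per arm, rACC minus amygdala rejects 93% of the time with amygdala 0 and about 21% with -0.5. The two contrasts thus move in opposite directions when the amygdala falls, and the omnibus test hardly distinguishes the two cases. The contrasts describe relative change. None of them bounds the amygdala decrease itself.

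**Step 4: what an interval rule would deliver.** With margin 0.5 SD and no true change, the lower 95% limit for BATA minus MBCT exceeds -0.5 in 41% of trials at 25 per arm, 77.5% at 60 and 90% at 85.

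**The case against.** **The region comparisons test specificity.** In part they do. If both post-hoc contrasts had to be significant in the predicted directions, this would occur 86% of the time at 85 per arm with no amygdala change and about 21% with a 0.5 SD fall. That is real information on relative specificity. But the plan states no such joint rule, 21% is not strict error control, and at 25 per arm the rule rarely succeeds (13%).

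**The Aim 5 sample removes the problem.** It largely does for a 0.5 SD fall within BATA. Section 9.2 also expects about 90% to reach post-treatment assessment; at 94 per arm the between-arm miss is 7%. Smaller differences, the open direction and comparison, and the unknown number scanned remain.

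**These are predictions, and R61 is described as preliminary.** True, and the plan nowhere says that a non-significant test will count as confirmation. That is an inference from the absence of any other rule.

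**Stronger readings to avoid:**
- A reader might infer that the amygdala result entered the go/no-go decision, because the amygdala region is described in the same paragraph. Section 9.2 rests that decision on CN and rACC metrics, and the closing reference to the ROI analysis is naturally read as a contrast with the whole-brain work that follows.
- A reader might infer that no estimand exists. Only direction and comparison are missing.
- A reader might infer that amygdala activation should fall in both arms, because MBCT was "chosen because its mechanisms of action are hypothesized to impact different brain mechanisms than BATA". That Synopsis text does not mention the amygdala or predict a fall under MBCT.

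**Conclusion.** The concern holds in a limited form. Aims 1 and 5 attach a confirmatory conclusion to an absence of change, while the analysis contains only tests of difference, the power statement omits the amygdala, and direction and comparison are unsettled. A non-significant result at 25 per arm would be weak evidence. At 85 per arm a 0.5 SD fall within BATA would rarely be missed, so for an effect of that size the weakness lies mainly in R61, though smaller between-arm differences remain hard to exclude.

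These sizes rest on an assumed fall in units of the SD of change, with no covariate gain, because the documents give no amygdala variance. The absence of a rule for claiming specificity does not depend on those assumptions.

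**What to change.** Keep the planned model for CN and rACC. For the amygdala:
- State one direction (no decrease, or no impact) and one comparison (within BATA, or BATA minus MBCT), and use them consistently in the Synopsis and Sections 3, 4.1 and 9.1.
- Report the change with confidence intervals both for BATA minus MBCT and within BATA. Note that the within-BATA change is uncontrolled and includes any time or retest effect. For that reason it is reported alongside, and is not made an automatic second hurdle.
- For Aim 5, claim specificity only if the interval for the chosen comparison excludes a decrease larger than a margin justified before that analysis. Aim 5 includes the R61 participants, so the margin should not be drawn from their amygdala data. Otherwise, report the intervals and say that specificity is not established.
- For R61, which Sections 4.1 and 4.2 show has ended, report the intervals and use the softer wording. A margin set now would probably be post hoc.
- State the confidence level and reconcile it with the alpha of 0.025.

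The cost is SAP wording and two intervals, with no new data. The harder part is justifying a margin, and specificity may prove unsupportable at the number actually scanned (Step 4). Choosing no impact costs more. With margin 0.5 SD, a 90% interval between arms and 25 per arm, success under no true change drops from 54% (lower limit only) to about 10% (both limits).
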